9.3.1.1. Overall Survival (OS)

OS is defined as the time from the start of treatment with avelumab plus axitinib to the date of death due to any cause. If there are no clinical records of death, the date when the patient was last documented to be alive will be confirmed based on medical records. The data will be censored at the date of last contact.

9.3.1.2. Objective response rate (ORR)

The ORR is defined as the proportion of patients with a documented BOR (complete response (CR) or partial response (PR)) by the investigator during treatment with avelumab plus axitinib as first-line therapy. The BOR is defined as the best tumor response recorded during the observation period. The definitions of tumor responses are as follows:

Complete or PR as the best adjudication result (CR > PR > stable disease [SD] > progressive disease [PD], not Evaluable[NE]) complies with the RECIST tumor assessment guidelines as closely as possible in clinical practice.

9.3.1.3. Time to treatment discontinuation (TTD)

TTD is defined as the time from the start of treatment with avelumab plus axitinib to the end of treatment due to any cause except the effectiveness of the treatment.

9.4. Data sources

As this is a retrospective study, all data are to be collected from the patient medical records at the participating study sites.

9.5. Study size

This descriptive study aims to describe the demographic and baseline characteristics for patients treated with avelumab plus axitinib as first-line therapy for mRCC, rather than testing any predefined hypothesis. Since all analyses are descriptive, sample size calculations are not applicable.

The expected number of patients is approximately 150 patients in total. However, this number should be considered flexible.

9.6. Data management

Investigators will complete electronic case report forms (eCRFs) based on medical charts reviews using electronic data capture (EDC). After completion, the eCRFs are transferred to a single electronic database. Only the de-identified and anonymized data will be included in this database.

When receiving a query from the sponsor regarding the completed eCRF (ie, a data clarification form [DCF]), investigators will reconfirm the information in the source documents, fill out the DCF as required, and submit the DCF.

9.6.1. Case report forms (CRFs) /Data collection tools (DCTs)/ Electronic data record

As used in this protocol, the term CRF should be understood to refer an electronic data record in this study.

A CRF is required and should be completed for each included patient. The completed original CRFs are the sole property of Pfizer and should not be made available in any form to third parties, except for authorized representatives of Pfizer or appropriate regulatory authorities, without written permission from Pfizer. The investigator shall ensure that the CRFs are securely stored at the study site in encrypted electronic form and will be password protected to prevent access by unauthorized third parties.

The investigator has ultimate responsibility for the collection and reporting of all clinical, safety, and laboratory data entered on the CRFs and any other data collection forms (source documents) and ensuring that they are accurate, authentic/original, attributable, complete, consistent, legible, timely (contemporaneous), enduring, and available when required. The CRFs must be signed by the investigator or by an authorized staff member to attest that the data contained on the CRFs are true. Any corrections to entries made in the CRFs or source documents must be dated, initialed, and explained (if necessary) and should not obscure the original entry.

The source documents are the hospital or the physician's chart. In these cases, data collected on the CRFs must match those charts.

9.6.2. Record retention

To enable evaluations and/or inspections/audits from regulatory authorities or Pfizer, the investigator agrees to keep records, including the identity of all participating patients (sufficient information to link records, eg, CRFs and hospital records), all original signed informed consent/assent documents, copies of all CRFs, safety reporting forms, source documents, detailed records of treatment disposition, and adequate documentation of relevant correspondence (eg, letters, meeting minutes, and telephone call reports). The records should be retained by the investigator according to local regulations or as specified in the clinical study agreement (CSA), whichever is longer. The investigator must ensure that the records continue to be stored securely for so long as they are retained.

If the investigator becomes unable for any reason to continue to retain study records for the required period (eg, retirement, relocation), Pfizer should be prospectively notified. The study records must be transferred to a designee acceptable to Pfizer, such as another investigator, another institution, or to an independent third party arranged by Pfizer.

Study records must be kept for a minimum of 15 years after completion or discontinuation of the study, unless study site and Pfizer have expressly agreed to a different period of retention via a separate written agreement or as required by applicable local regulations.

The investigator must obtain Pfizer's written permission before disposing of any records, even if retention requirements have been met.

9.7. Data analysis

Detailed methodology for summary and statistical analyses of data collected in this study will be documented in a SAP, which will be dated, filed and maintained by the sponsor. The SAP may modify the plans outlined in the protocol; any major modifications of primary endpoint definitions or their analyses would be reflected in a protocol amendment. The SAP must be fixed prior to data lock. The analysis is to be performed after the data lock.

9.7.1. Analysis Population

Full analysis set (FAS): The FAS will consist of patients who meet the inclusion criteria and do not meet the exclusion criteria.

Efficacy analysis set: The efficacy analysis set is a subset of the FAS that includes patients whose index date is prior to 30 April 2022 to ensure a 6-months follow-up period.

Subgroups: A subgroup analysis will be considered, including but not limited to subgroups categorized by IMDC risk group, age (≥ 75 years or < 75 years), and the presence or absence of corticosteroid administrations for irAE in the medical record.

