9.3. Variables

Only data available from the treating physician's routine clinical assessments as per local standard of care will be collected. Variables and data sources are described in [Table 1](#). Detailed definitions will be included in the Statistical Analysis Plan (SAP).

Table 1. Variables in this study

Variable	Role	Data source(s)	Operational definition
Patient characteristics	Baseline characteristics, sub-group identifiers	Patient medical records	Patient characteristics at baseline, including the most recent data prior to initial treatment with avelumab plus axitinib: age, sex, height, weight, body mass index, smoking history, comorbidities, concomitant use of drugs, Eastern Cooperative Oncology Group (ECOG) performance status, pathological diagnosis (Fuhrman grade, TNM classification, histological type sarcomatoid component), the number of metastatic organs and the site of metastasis, the presence or absence of

PFIZER CONFIDENTIAL

CT24-WI-GL02-RF02 4.0 Non-Interventional Study Protocol Template For Secondary Data Collection Study 01-Jun-2022

			
nephrectomy, laboratory data (C-reactive protein (CRP), estimated glomerular filtration rate (eGFR), proteinuria), and International Metastatic RCC Database Consortium (IMDC) risk score
 
 - <1 year from time of diagnosis to systemic therapy - Karnofsky Performance Status <80% - Hemoglobin < lower limit of normal - Corrected calcium > upper limit of normal - Neutrophils > upper limit of normal - Platelets > upper limit of normal)
Avelumab plus axitinib treatment patterns	Exposure, outcome, sub-group identifier	Patient medical records	Start and end date of avelumab plus axitinib as first-line therapy.
Management of AE	Exposure, outcome, sub-group identifier	Patient medical records	Corticosteroid treatment for irAEs occurring during treatment with avelumab plus axitinib (drug, dose), the presence or absence of pre-medication and treatment for infusion-related reactions.
Subsequent treatment patterns	Exposure, outcome, sub-group identifier	Patient medical records	Subsequent treatment (drug name and duration of use for second-line therapy).
Clinical outcomes	Outcome	Patient medical records	
BOR, assessment of disease progression, real-world PFS, OS, ORR, TTD.
 
For the patients not nephrectomized at baseline: BOR for the primary lesion, the date of nephrectomy after administration of avelumab plus axitinib.

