### **4.3 OTHER ANALYSIS SET**

#### Efficacy analysis set

*The efficacy analysis set is a subset of the FAS comprising patients whose index date is prior to April 30, 2022, to ensure a 6-month follow-up period.*

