### **4.4 SUBGROUPS**

*A subgroup analysis will be considered, including but not limited to the subgroups categorized by IMDC (International Metastatic RCC Database Consortium) risk group, age ( $\geq 75$  years or  $< 75$  years), and the administration of corticosteroid therapy for irAE in the medical record.*

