#### 5.4 COVARIATES

- Age (2 categories)
- Body mass index (BMI) (3 categories)
- C-reactive protein (CRP) (3 categories)
- Estimated glomerular filtration rate (eGFR) (3 categories)
- Smoking history
- ECOG Performance Status
- ECOG Performance Status ①
- ECOG Performance Status ②
- Tumor histological type
- Presence or absence of sarcomatoid component
- Fuhrman grade (3 categories)
- Performance of nephrectomy
- Metastatic site: Lung

PFIZER CONFIDENTIAL

- Metastatic site: Liver
- Metastatic site: Bone
- Metastatic site: Brain
- Metastatic site: Regional lymph node
- Metastatic site: Distant lymph node
- Metastatic site: Other
- Number of metastatic organs (5 categories)
- Presence or absence of clinically important comorbidities
- Presence or absence of clinically important concomitant drugs
- Less than 1 year from diagnosis to the initiation of systemic therapy
- Karnofsky Performance Status <80%
- Hemoglobin value below the lower normal limit
- Corrected calcium value above the upper normal limit
- Neutrophil count above the upper normal limit
- Platelet count above the upper normal limit
- IMDC risk group
- Administration of corticosteroid therapy for irAEs

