### **Analysis of secondary objectives**

#### **7.2.2.2 Real-world progression-free survival**

Source : Efficacy analysis set  
 population  
 Endpoint : Real-world PFS  
 Analysis content : For the endpoint, the median and its 95% confidence interval will be calculated using the Kaplan–Meier method. In addition, the Kaplan–Meier curve will be plotted, and the PFS rate for every 12 months and its 95% confidence interval will be calculated. Greenwood’s formula will be used to calculate the confidence interval for the PFS rate. In addition, the number of event-onset cases and the number of censored cases will be presented. A frequency table (number of cases, percentage (%)) will be created, considering the reasons for the event and reasons for censoring. In order to evaluate the observation period, the median observation period and its 95% confidence interval will be calculated by estimating the reverse Kaplan-Meier curve in which censoring patients are regarded as patients with events and patients with events are regarded as censoring patients.

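### The corticosteroid-for-irAE subgroup is fixed after index: if PFS or OS is split by it from treatment start, immortal time favours the steroid group, and no readable passage sets a timing rule

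*Protocol*

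**What the plan says.** Protocol 9.7.1 says that subgroup analyses will be considered and names three: IMDC risk group, age at a cut of 75 years, and "the presence or absence of corticosteroid administrations for irAE in the medical record". SAP 4.4 has the same list, ending with "the administration of corticosteroid therapy for irAE in the medical record". Neither gives a time window. SAP 5.4 lists "Administration of corticosteroid therapy for irAEs" among covariates that are otherwise mostly baseline items. SAP 7.2.2.8 codes it once per patient as no, yes or unknown.

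Protocol Table 1 (section 9.3) describes the data item as "Corticosteroid treatment for irAEs occurring during treatment with avelumab plus axitinib (drug, dose", so the irAE arises after treatment has begun.

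The outcome clocks start earlier. Protocol 9.3.1.1 states that "OS is defined as the time from the start of treatment with avelumab plus axitinib to the date of death due to any cause", and real-world PFS has the same origin. SAP 7.2.2.2 and 7.2.2.3 use Kaplan-Meier medians and rates at 12-month steps; for PFS, "the PFS rate for every 12 months and its 95% confidence interval will be calculated". Both outcomes use the efficacy analysis set (SAP 4.3): "The efficacy analysis set is a subset of the FAS comprising patients whose index date is prior to April 30, 2022".

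No readable passage gives a landmark, a time-dependent method or another timing rule. SAP Appendix 2, where method detail would sit, is marked not applicable. Text is blacked out in protocol 8.2 and 9.7.2, in SAP 2.2, after SAP 5.2 and after SAP 7.2.2.10.

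**The concern.** Two of the three named subgroups are known at index. The third is not. A patient who progresses or dies early has little time to develop an irAE and receive steroids, so early events collect in the no group. A yes patient has usually survived, event-free and on treatment, until the irAE. Counting that interval from treatment start credits the steroid group with time in which it could not have had an event. This is immortal-time bias, and it arises even if steroids have no effect.

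Curves by steroid use would then show an advantage made partly or wholly by the grouping, and a reader could not tell how much. The study tests no hypotheses, so the harm is a misleading display with 95% intervals, not a false test. The primary objective, the overall Kaplan-Meier estimates and the steroid-use tables in SAP 7.2.2.8 do not depend on the split.

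**Working it through.** The plan gives no figure to reproduce: protocol 9.5 says that sample size calculations do not apply. The check asks how large the artefact is when steroids have no effect.

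**Inputs from the documents**
- PFS median 13.8 months (pivotal trial, protocol section 7): λ = ln 2 / 13.8 = 0.0502 per month.
- Follow-up to 31 October 2022. The last efficacy-set index date, 29 April 2022, gives 185 days (6.1 months); the first, 20 December 2019, gives 34.4 months.
- Size: "The expected number of patients is approximately 150 patients in total". With uniform index dates, the efficacy set is 150 × 862 / 1,033 = 125.

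**Assumptions, not in the documents**
- Steroid onset is independent of outcome: (a) 30% of patients susceptible, median onset 1 month; (b) 30% susceptible, mean onset 4 months; (c) all susceptible at a constant rate, median 24 months, an extreme case.
- Therapy ends at progression, or half of patients continue for a mean of 6 months beyond it.
- OS median 36 months.
- Not modelled: steroids begun after therapy stopped, and censoring at nephrectomy, second-line start or an early last visit.

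**Closed form for case (b), ignoring censoring, therapy ending at progression.** Steroid rate μ = 1/4 = 0.25.
- P(steroid before event | susceptible) = μ/(μ+λ) = 0.25/0.3002 = 0.833.
- P(PFS > 12) = exp(−12 × 0.0502) = 0.547.
- P(PFS > 12 and steroid before event | susceptible) = 0.547 − [λ/(λ+μ)] exp(−12(λ+μ)) = 0.547 − 0.167 × 0.027 = 0.543.
- 12-month PFS, yes group: 0.543/0.833 = 65%.
- 12-month PFS, no group: (0.547 − 0.3 × 0.543)/(1 − 0.3 × 0.833) = 0.384/0.750 = 51%.

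The true rate is 55% in both groups.

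**Simulation with follow-up cut off as above** (yes vs no; therapy ends at progression / half continue):

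| Case | PFS event-rate ratio | 12-month PFS |
|---|---|---|
| (a) | 0.86 / 0.92 | 59% vs 53% / 57% vs 54% |
| (b) | 0.71 / 0.80 | 65% vs 51% / 61% vs 52% |
| (c) extreme | 0.43 / 0.52 | 78% vs 46% / 72% vs 47% |

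At n = 125 the steroid group has the higher 12-month PFS rate in 63–70% (a), 80–89% (b) and over 99% (c) of null studies. With 20% or 40% susceptible and therapy ending at progression, the hazard ratio is 0.84–0.88 at a median onset of 1 month, 0.67–0.72 at 3 months and 0.57–0.63 at 6 months.

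For OS, across four assumptions on when therapy ends and how death relates to progression, the ratio is 0.86–0.92 (a), 0.72–0.79 (b) and 0.41–0.56 (c).

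**With a 3-month landmark**
- PFS: ratio 0.99–1.01; the steroid group has the higher 12-month rate in 50–52% of null studies. Retained: exp(−3 × 0.0502) = 86%. At 6 months, exp(−6 × 0.0502) = 74%.
- OS among all patients alive: about 1.0 if progression and death are independent, but 0.90–0.92 if death follows progression and therapy ends at progression. Restricted to patients still on first-line therapy, about 1.0 in both.
- OS with a time-dependent covariate: 0.88, 0.77 and 0.60 (a, b, c) when death follows progression, so it is no substitute there.

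**TTD, case (b).** If 0%, 10% or 25% of steroid starts end treatment at once, the ever/never ratio is 0.71, 0.83 or 1.07. At 25%, a time-dependent ratio is 1.62 or 0.88, depending on whether a stop on the steroid date counts as exposed, and the landmark gives about 0.94.

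**The case against.** **No split is committed to.** Both documents say only that subgroups will be considered, and steroid use is itself a descriptive objective. The subgroup might serve only to describe those patients. A reader might infer that the plan contains a biased comparison; the readable text does not support that. This stands, and it makes the point conditional.

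**Redacted text may hold the rule.** Blacked-out text follows the Kaplan-Meier paragraph in protocol 9.7.2, and the SAP contents list shows a redacted entry after 7.2.2.10. No readable analysis uses the SAP 5.4 covariates, so their use may well be described there. It would be wrong to say that a timing rule is missing from the plan; it is only not readable.

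**A yes patient need not be on therapy when steroids start.** In Table 1, the reference to treatment attaches to the irAE, not to the first steroid dose. Steroids begun after stopping for an irAE would also count. This stands. The claim is that most yes patients remained under treatment until an irAE, not that all were treated until the steroid.

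**The size is assumed.** Correct. In case (a) the 12-month difference is only 3 to 6 points, against a standard deviation of 9 to 11 points at n = 125. Immortal time pushes one way for PFS and OS, but confounding could add to or offset it.

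**A caveat would do.** A note that the grouping is post-index warns the reader but leaves the biased curves in place. It suits non-survival tables, or a case in which no start dates exist.

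**Conclusion.** The concern holds conditionally. If PFS or OS is shown by ever/never corticosteroid use for irAE, with Kaplan-Meier from treatment start, immortal time favours the steroid group. The PFS event-rate ratio under no effect is about 0.7–0.9 in the main scenarios and 0.4–0.5 in the extreme one. These figures rest on assumed steroid frequency and onset, exponential PFS with the pivotal-trial median, and steroid onset unrelated to prognosis. They show plausible size and are not predictions.

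Two further inferences are not supported. The same direction cannot be claimed for TTD, because SAP 5.1 lists adverse events as a reason for stopping, and the sign changes with how often steroid start and stopping coincide. Nor does a landmark cure everything: for OS among all patients alive, some bias can remain, and for TTD no simple method settles the tie.

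This is a point to consider: an optional subgroup, a real hazard if it is used, and a short remedy.

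**What to change.** First check whether redacted text already sets a timing rule. If it does, a cross-reference in SAP 4.4 is enough. If not:

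1. **SAP 4.4.** State that any PFS or OS result by this variable will use a pre-stated landmark, for example 3 months after index. Group patients by steroid use up to that date, among those event-free (PFS) or alive (OS) and under observation.
2. **OS sensitivity analysis.** Repeat among patients still on first-line therapy at the landmark, noting that this excludes patients who stopped because of an irAE.
3. **SAP 5.4.** Mark the item as post-index.
4. **TTD.** Make no comparison by this variable.
5. **Dates.** SAP 7.2.2.8 summarises steroid duration in days, which implies start dates, but protocol Table 1 mentions only drug and dose. If start dates were not collected, make no time-to-event comparison by this variable.
6. **Other tables, such as ORR by steroid use.** Label the grouping as post-index and not causal.

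**Cost.** A few sentences and a small programming change, with no new data if start dates exist. Under the assumptions above, the 3-month landmark loses about 14% of patients for PFS. The OS on-therapy restriction loses 6–19%. Of about 125 patients, the steroid group falls from about 31–38 (ever) to about 9–28 (by 3 months and still event-free). In the OS sensitivity analysis it would be about 7–21 if a quarter of steroid starts end treatment. The standard deviation of the 12-month PFS difference rises from 9–11 to 11–19 points, so the landmark estimate will be imprecise, and it applies only to patients still at risk at the landmark.

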9.7.2. Analysis Methods

Continuous variables will be summarized using descriptive statistics (ie, the number of non-missing and missing values [ie, n (missing)], the mean, median, standard deviation [SD], minimum and maximum, and the first and third quartiles).

Qualitative variables will be summarized using frequency count and percentages.

For the time-to-event endpoints (for eg, OS, TTD and real-world PFS), Kaplan-Meier estimates will be presented together with a summary of the associated statistics including the median time with 2-sided 95% CIs. In particular, the survival rate at several time points will be estimated along with the corresponding 2-sided 95% CIs. These endpoints will be displayed graphically.

CCI

9.8. Quality control

The sponsor will train the investigators and study site staff in regard to the protocol, eCRFs, and any applicable study processes via an on-site training visit or web training. Any new information relevant to the performance of this study will be forwarded to the investigators and the study site staff during the course of the study. Remote data monitoring will be conducted during the study period to ensure the timely reporting of data, data integrity, and consistency. The eCRFs for all included patients will be made available to the remote data monitor for review. The study sites may be queried and should be capable of resolving any issues that may arise during the course of the study. On-site monitoring visits have not been planned for this study. The data manager from the contract research organization commissioned by the sponsor prepares and submits the data monitoring report to the sponsor before the database is locked. The data monitoring report includes the number of cases, the completion of eCRF, queries, and the possible issue or protocol deviation.

9.9. Limitations of the research methods

- This study is retrospective in nature. Therefore, only existing data reported in patient records is available for the present research. Missing data may affect the estimation accuracy.
- High-volume centers were preferentially selected for this study, potentially leading to site selection and outcome reporting biases. Therefore, the study results may not accurately reflect clinical outcomes for all Japanese centers.
- The evaluation of disease response may differ at each site, and measurement errors may be included in the estimated values.

